6.2 Antitumor Effect- Solid Tumors

Response and progression will be evaluated in this study using the new international criteria proposed by the Response Evaluation Criteria in Solid Tumors (RECIST) Committee [JNCI 92(3):205-216, 2000]. Changes in only the largest diameter (unidimensional measurement) of the tumor lesions are used in the RECIST v1.1 criteria.

6.2.1 Definitions

Evaluable for toxicity. All patients will be evaluable for toxicity from the time of their first treatment with study drug.

Evaluable for objective response. Only those patients who have measurable disease present at baseline, have received at least one cycle of therapy, and have had their disease re-evaluated will be considered evaluable for response. These patients will have their response classified according to the definitions stated below. (Note: Patients who exhibit objective disease progression prior to the end of cycle 1 will also be considered evaluable.)

CONFIDENTIAL

This material is the property of the [UC Irvine Chao Family Comprehensive Cancer Center](#). Do not disclose or use except as authorized in writing by the study sponsor.

Evaluable Non-Target Disease Response. Patients who have lesions present at baseline that are evaluable but do not meet the definitions of measurable disease, have received at least one cycle of therapy, and have had their disease re-evaluated will be considered evaluable for non-target disease. The response assessment is based on the presence, absence, or unequivocal progression of the lesions.

6.2.2 **Disease Parameters**

Measurable disease. Measurable lesions are defined as those that can be accurately measured in at least one dimension (longest diameter to be recorded) as ≥ 20 mm with conventional techniques (CT, MRI, x-ray) or as ≥ 10 mm with spiral CT scan. All tumor measurements must be recorded in millimeters (or decimal fractions of centimeters).

Note: Previously irradiated lesions are non-measurable except in cases of documented progression of the lesion since the completion of radiation therapy.

Non-measurable disease. All other lesions (or sites of disease), including small lesions (longest diameter <20 mm with conventional techniques or <10 mm using spiral CT scan), are considered non-measurable disease. Bone lesions, leptomeningeal disease, ascites, pleural/pericardial effusions, lymphangitis cutis/pulmonis, inflammatory breast disease, abdominal masses (not followed by CT or MRI), and cystic lesions are all non-measurable.

Note: Cystic lesions that meet the criteria for radiographically defined simple cysts should not be considered as malignant lesions (neither measurable nor non-measurable) since they are, by definition, simple cysts.

'Cystic lesions' thought to represent cystic metastases can be considered as measurable lesions, if they meet the definition of measurability described above. However, if non-cystic lesions are present in the same patient, these are preferred for selection as target lesions

Target lesions. All measurable lesions up to a maximum of 3 lesions per organ and 6 lesions in total, representative of all involved organs, should be identified as **target lesions** and recorded and measured at baseline. Target lesions should be selected on the basis of their size (lesions with the longest diameter) and their suitability for accurate repeated measurements (either by imaging techniques or clinically). A sum of the longest diameter (LD) for all target lesions will be calculated and reported as the baseline sum LD. The baseline sum LD will be used as reference by which to characterize the objective tumor response.

Non-target lesions. All other lesions (or sites of disease) including any measurable lesions over and above the 6 target lesions should be identified as **non-target lesions** and should also be recorded at baseline. Measurements of these lesions are not required, but the presence or absence of each should be noted throughout follow-up.

6.2.3 **Methods for Evaluation of Measurable Disease**

All measurements should be taken and recorded in metric notation using a ruler or calipers. All baseline evaluations should be performed as closely as possible

CONFIDENTIAL

This material is the property of the [UC Irvine Chao Family Comprehensive Cancer Center](#). Do not disclose or use except as authorized in writing by the study sponsor.

to the beginning of treatment and never more than 28 days before the beginning of the treatment.

The same method of assessment and the same technique should be used to characterize each identified and reported lesion at baseline and during follow-up. Imaging-based evaluation is preferred to evaluation by clinical examination when both methods have been used to assess the antitumor effect of a treatment.

Measurements should be performed on schedule even in the event of study treatment delay or omission.

Imaging delays due to patient deterioration will not be considered a protocol deviation.

Conventional CT and MRI. These techniques should be performed with cuts of 10 mm or less in slice thickness contiguously. Spiral CT should be performed using a 5 mm contiguous reconstruction algorithm. This applies to tumors of the chest, abdomen, and pelvis. MRI is also acceptable in certain situations (e.g. for body scans). Scans will be done within 28 days prior to cycle 1 and after that every 8 weeks (+/- 7 days) until end of treatment.

PET-CT At present, the low dose or attenuation correction CT portion of a combined PET-CT is not always of optimal diagnostic CT quality for use with RECIST measurements. However, if the site can document that the CT performed as part of a PET-CT is of identical diagnostic quality to a diagnostic CT (with IV and oral contrast), then the CT portion of the PET-CT can be used for RECIST measurements and can be used interchangeably with conventional CT in accurately measuring cancer lesions over time. Note, however, that the PET portion of the CT introduces additional data which may bias an investigator if it is not routinely or serially performed.

Ultrasound **Ultrasound is not useful in assessment of lesion size and should not be used as a method of measurement.** Ultrasound examinations cannot be reproduced in their entirety for independent review at a later date and, because they are operator dependent, it cannot be guaranteed that the same technique and measurements will be taken from one assessment to the next. If new lesions are identified by ultrasound in the course of the study, confirmation by CT or MRI is advised. If there is concern about radiation exposure at CT, MRI may be used instead of CT in selected instances.

Cytology, Histology. These techniques can be used to differentiate between partial responses (PR) and complete responses (CR) in rare cases (e.g., residual lesions in tumor types, such as germ cell tumors, where known residual benign tumors can remain).

The cytological confirmation of the neoplastic origin of any effusion that appears or worsens during treatment when the measurable tumor has met criteria for response or stable disease is mandatory to differentiate between response or stable disease (an effusion may be a side effect of the treatment) and progressive disease.

CONFIDENTIAL

This material is the property of the [UC Irvine Chao Family Comprehensive Cancer Center](#). Do not disclose or use except as authorized in writing by the study sponsor.

6.2.4 Response Criteria

6.2.4.1 Evaluation of Target Lesions

Complete Response (CR): Disappearance of all target lesions, determined by two separate observations conducted not less than 4 weeks apart. There can be no appearance of new lesions.

Partial Response (PR): At least a 30% decrease in the sum of the longest diameter (LD) of target lesions, taking as reference the baseline sum LD. There can be no appearance of new lesions.

Progressive Disease (PD): At least a 20% increase in the sum of the LD of target lesions, taking as reference the smallest sum LD recorded since the treatment started, or the appearance of one or more new lesions.

Stable Disease (SD): Neither sufficient shrinkage to qualify for PR nor sufficient increase to qualify for PD, taking as reference the smallest sum LD since the treatment started.

6.2.4.2 Evaluation of Non-Target Lesions

Complete Response (CR): Disappearance of all non-target lesions and normalization of tumor marker level.

Incomplete Response/Stable Disease (SD): Persistence of one or more non-target lesion(s) and/or maintenance of tumor marker level above the normal limits.

Progressive Disease (PD): Appearance of one or more new lesions and/or unequivocal progression of existing non-target lesions

6.2.5 Duration of Response

Duration of overall response: The duration of overall response is measured from the time measurement criteria are met for CR or PR (whichever is first recorded) until the first date that recurrent or progressive disease is objectively documented (taking as reference for progressive disease the smallest measurements recorded since the treatment started).

The duration of overall CR is measured from the time measurement criteria are first met for CR until the first date that recurrent disease is objectively documented.

Duration of stable disease: Stable disease is measured from the start of the treatment until the criteria for progression are met, taking as reference the smallest measurements recorded since the treatment started.

6.2.6 Objective Response Rate

ORR is defined as the percentage of patients who have achieved an objective confirmed overall complete response (CR) or partial response (PR) based on RECIST version 1.1 guidelines.

CONFIDENTIAL

This material is the property of the [UC Irvine Chao Family Comprehensive Cancer Center](#). Do not disclose or use except as authorized in writing by the study sponsor.

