Statistical Methodology	Efficacy of the study will be measured by estimating the objective response rate (CR, PR) in the breast and/or the axillary lymph nodes or determining if the combination of Abemaciclib and Fulvestrant increases the percentage of patients who undergo breast conserving surgery. The latter will be measured by constructing 95% CI. We plan to use survival analysis methods such as Kaplan-Meier estimates of survival probability for univariate analysis and log rank tests in order to evaluate differences among distinct patient characteristics such as age group for recurrence or disease-free survival. For multivariate analysis we plan to use the Cox proportional hazards model in order to examine survival adjusted for a number of covariates. Safety and toxicity will be examined by the incidence of treatment-emergent, treatment-related adverse events (TRAEs), and serious adverse events (SAE). Consequently, side effects and adherence to the protocol will be closely monitored throughout the duration of the study. Interim analyses will be performed to assess the side effects. Contingency tables will be constructed to compare the proportion of patients with side effects by study characteristics (e.g. age, race ethnicity and other clinical and epidemiologic characteristics). Distributions of all data items will be generated and examined for the presence of outliers. This will be to assess the general form of the distributions, and to compute measures of central tendency and variability. Trellis graphics will be used for data display including histograms, boxplots, and Q-Q normal plots. In addition, we plan to examine if genomic analysis of patient-matched breast tissue samples and serial mutational tracking of circulating tumor DNA can identify new mechanisms of endocrine resistance and the way Abemaciclib overcomes this resistance. For the analyses of matched pair tissue data, we will use paired t tests or Wilcoxon sign rank statistical analysis in order to test differences in recurrent and treated breast tissue. We plan to measure absolute values and changes in circulating tumor DNA and correlate them with endocrine resistance. If serial monitoring of ctDNA can provide markers of resistance, we will quantify endocrine resistance as a composite outcome that will be computed as dichotomous variable if it happens (yes or no) and at what time interval during the study. We will start by using frequency table analysis to examine the relationship between resistance or sensitivity and specific mutations.

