2.4 Endpoints

The primary endpoint is pathological complete response (pCR) as defined by no evidence of tumor cells in the final surgical specimen
The secondary endpoints are ORR per RECIST 1.1 criteria, recurrence disease-free and incidence of AEs

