3.1 Inclusion Criteria

- 3.1.1 Patients must have a diagnosis of HR+ breast cancer. To fulfill the requirement of HR+ disease, a breast cancer must express, by immunohistochemistry (IHC), at least one of the hormone receptors (ER, progesterone receptor [PgR]) as defined in the relevant American Society of Clinical Oncology (ASCO)/College of American Pathologists (CAP) Guidelines (Hammond et al. 2010):
 - For ER and PgR assays to be considered positive, $\geq 1\%$ of tumor cell nuclei must be immunoreactive by immunohistochemistry (IHC) (Hammond et al. 2010).
- 3.1.2 Patients must have Loco regional breast cancer (Stage I, Stage II and stage III per AJCC 8th edition criteria for staging of breast cancer)
- 3.1.3 Patients must have localized recurrence while on adjuvant endocrine therapy
- 3.1.4 Patients must have any known molecular evidence of endocrine resistance by next generation sequencing
- 3.1.5 Age ≥ 18 years.
- 3.1.6 ECOG performance status 0-1
- 3.1.7 Have post-menopausal status as defined by following:
 - Prior bilateral oophorectomy
 - Age ≥ 60 years
 - Age < 60 and amenorrheic (non-treatment-induced amenorrhea secondary to tamoxifen, toremifene, ovarian suppression, or chemotherapy) for at least 12 months. Follicle-stimulating hormone (FSH) and estradiol must be in the postmenopausal range.
- 3.1.8 Have at least one measurable disease as defined per RECIST 1.1
- 3.1.9 Adequate organ and marrow function as defined below:
 - Hemoglobin* > 8 g/dL
 - Absolute neutrophil count $\geq 1,500/\text{mcL}$
 - Platelets $\geq 100,000/\text{mcL}$
 - Total bilirubin $\leq 1.5 \times$ institutional ULN

Patients with Gilbert's syndrome with a total bilirubin ≤ 2.0 times ULN and direct bilirubin within normal limits are permitted

 - AST (SGOT)/ALT (SPGT) $\leq 2.5 \times$ institutional ULN
 - Creatinine $\leq 1.5 \times$ institutional ULN

**Patients may receive transfusion of packed red blood cells (PRBC) to achieve this hemoglobin level at the discretion of the investigator; however, initial study drug treatment must not begin earlier than the day after the PRBC transfusion.*

CONFIDENTIAL

This material is the property of the [UC Irvine Chao Family Comprehensive Cancer Center](#). Do not disclose or use except as authorized in writing by the study sponsor.

- 3.1.10 Able to swallow oral medications

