5.3.2 Within 30 days after treatment termination

- Physical exam, vital signs
- Hematology
- Serum chemistries
- Adverse Events
- Review previous and current concomitant medications

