10.2 Sample Size and Accrual and Data Analyses Plans

Tumor Registry data at UCIMC shows that we have had 960 patients with Hormone Receptor positive breast cancer from 2012-2017. The 2018 data is currently not populated by the tumor registry. Similarly, from 1/1/14 to 6/14/2019, there have been 456 patients accrued in breast cancer trials out of which, 155 patients were enrolled in treatment trials. In order to obtain 30 evaluable breast cancer participants to examine the primary hypothesis, we will need to screen 680 invasive breast cancer patients (this is clearly possible due to the cohort of 960 patients from 2012-2017). Based on the data from California Cancer Registry and estimated percentage of recurrence, we estimate that approximately around 10% of 680 invasive breast cancer patients are post-menopausal, have histologically been confirmed with HR+, have localized non-metastatic breast cancer and will have recurrence. Of the 68 patients, we estimate that there are 59 (87% of 68) patients who are also on adjuvant endocrine therapy. The mutation ESR1 is

CONFIDENTIAL

This material is the property of the [UC Irvine Chao Family Comprehensive Cancer Center](#). Do not disclose or use except as authorized in writing by the study sponsor.

detected in 11-54% of patients with advanced breast cancer especially during the progression of hormonal therapy. Therefore, we estimate that there are 32 (54% of 59) patients who have ESR1 gene mutation/any known molecular evidence of endocrine resistance. To take into account of 5% attribution, we will need to enroll 32 subjects to receive the study treatment to ensure that there are 30 evaluable breast cancer participants. The plan of enrollment is over a four-year period. Hence, with the adequate number of patients justified from UCIMC tumor registry data and extending the period of enrollment from to four years, enrolling the sample size of 30 patients over a period of four years is feasible.

Table x1:Power and sample sizes of Simon's two-stage design

N	n ₁	r ₁	r ₂	Type 1 Error	Power	EN ₀	Probability of early stopping	p ₀	p ₁
29	10	1	5	0.0471	0.8051	15	0.7361	0.1	0.3

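### No denominator is named for ORR, and the only response set defined can drop patients who stop early, which would raise the rate

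*Combined protocol and SAP*

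**What the plan says.** **Endpoint.** In 2.4, "The secondary endpoints are ORR per RECIST 1.1 criteria". The Study Summary describes the analysis as "estimating the objective response rate (CR, PR) in the breast and/or the axillary lymph nodes", and 10.2 adds a 95% CI. Section 6.2.6 is the operative definition: "ORR is defined as the percentage of patients who have achieved an objective confirmed overall complete response (CR) or partial response (PR". None of these places names an analysis set.

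**Response set.** Section 6.2.1 admits "Only those patients who have measurable disease present at baseline, have received at least one cycle of therapy, and have had their disease re-evaluated". There is one exception: "Patients who exhibit objective disease progression prior to the end of cycle 1 will also be considered evaluable". Every patient should meet the first condition, because 3.1.8 requires it: "Have at least one measurable disease as defined per RECIST 1.1".

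**Imaging.** Sections 5.2.3 and 5.5 put breast MRI at 12-week intervals (±7 days) during treatment, and 5.5 ends it at maximum response or progression. The visit list in 5.3.2, headed "Within 30 days after treatment termination", contains no imaging. The table in 5.5 marks no MRI at End of Treatment or Surgery, and CT only at screening. Section 6.2.3, in its paragraph on conventional CT and MRI, gives 8-week intervals up to end of treatment.

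**Stopping.** Section 4.5 ends treatment at investigator-judged maximum response, at radiographic or symptomatic progression, for unacceptable adverse events, or on withdrawal, among other reasons. Section 4.8 says that patients are not replaced.

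**Confirmation.** Section 6.2.4.1 requires a CR to be seen twice, at least four weeks apart. It sets no such condition for PR.

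**The concern.** A response set that requires re-evaluation depends on what happens after treatment starts. Patients who leave before their first scan for toxicity, withdrawal or clinical worsening are unlikely to be responders. Removing them shrinks the denominator and leaves the numerator unchanged. The exception in 6.2.1 rescues only objective progression in the first cycle. It does not cover symptomatic progression, although 4.5 accepts that as a reason to stop.

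ORR is the first secondary objective and one of the two efficacy measures given a CI in 10.2. With no set named, two analysts could report different rates from the same data. The word *confirmed* in 6.2.6 adds a second, smaller ambiguity about the numerator.

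**Working it through.** **The plan's own figure.** The documents give no ORR target, precision or sample size. The nearest figure is enrolment in 10.2: 30/(1 − 0.05) = 31.6, rounded up to 32, which reproduces. It reads: "we will need to enroll 32 subjects to receive the study treatment to ensure that there are 30 evaluable breast cancer participants". That section needs those 30 for the primary hypothesis, which concerns pCR, so they are not the 6.2.1 imaging set. They are used below for illustration only.

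**Who can be left out.** One cycle is 28 days. The first post-baseline breast MRI is due at 12 × 7 = 84 days, or 84 − 7 = 77 days at the early edge of its window. A patient who completes cycle 1 and stops before about day 77 has met the one-cycle condition. She has had no scheduled on-treatment MRI and has none listed at end of treatment. Unless scanned off schedule, she is not evaluable under 6.2.1. A patient who stops within cycle 1 without objective progression is also left out.

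**Effect on the rate.** Let N be treated, m never re-evaluated and x responders, all of whom are among the re-evaluated.

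- Evaluable-set rate = x/(N − m); all-treated rate = x/N.
- Difference = x·m/[N(N − m)], which is positive whenever x and m are.

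Assumptions: N = 32. In the first three rows x is about 48.1% of those re-evaluated, the ORR that section 10.0 cites for this combination in advanced disease (0.481 × 30 = 14.4; × 29 = 13.9; × 26 = 12.5, taken as 13). The last two rows vary x at m = 2. Intervals are exact (Clopper-Pearson) 95%.

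| m | x | 6.2.1 set | All treated | Difference (points) |
|---|---|---|---|---|
| 2 | 14 | 14/30 = 46.7% (28.3–65.7) | 14/32 = 43.8% (26.4–62.3) | 2.9 |
| 3 | 14 | 14/29 = 48.3% (29.4–67.5) | 14/32 = 43.8% (26.4–62.3) | 4.5 |
| 6 | 13 | 13/26 = 50.0% (29.9–70.1) | 13/32 = 40.6% (23.7–59.4) | 9.4 |
| 2 | 6 | 6/30 = 20.0% | 6/32 = 18.8% | 1.3 |
| 2 | 20 | 20/30 = 66.7% | 20/32 = 62.5% | 4.2 |

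The CI half-width for 14/32 is (62.3 − 26.4)/2 = 18.0 points.

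**Confirmation.** Section 6.2.6 asks for confirmed CR or PR, 6.2.4.1 defines a second observation for CR only, and MRI ends at maximum response with surgery to follow. A response first seen on the last MRI before surgery therefore has no scheduled confirming scan. If confirmation extends to PR, each such response lowers ORR by 1/32 = 3.1 points or 1/30 = 3.3 points. If it does not, a CR seen once still meets the 30% PR criterion and no responder is lost. The text does not settle which reading applies.

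**Scan interval.** The 8-week statement in 6.2.3 matches nothing in 5.5, where breast MRI is 12-weekly and CT is at screening only.

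**The case against.** **The denominator is implied.** Section 6.2.1 says whose response is classified, and 6.2.6 sits under the same heading, so an analyst would probably use that set. This is fair, but it is the reading under which the rate is raised, and neither 6.2.6 nor 10.2 states it.

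**The effect is small and hypothetical.** This stands. The counts are assumed, and with two patients lost the gap is well inside the CI half-width. A wide interval does not settle who is counted, however. A reader might take 32 against 30 as the plan's expected ORR loss; the documents do not support that, because those figures concern pCR.

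**Most responses would be confirmed on schedule.** Also largely right. Judging that a maximum has been reached will often involve a later MRI, and 12 weeks exceeds the four-week minimum. A reader might infer that the plan systematically fails to confirm responses. The gap covers only those first seen on the final MRI, and only if PR needs confirmation. Section 6.2.6 also relies on the RECIST 1.1 guideline, so the absence of a PR rule is shown for the protocol's own text only.

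**The 8-week text may not concern breast MRI.** Its paragraph refers to tumors of the chest, abdomen and pelvis. A reader might infer two rival breast MRI schedules, with second scans at week 16 or week 24; the text does not clearly support this. Even if it did apply, the first scan would be due no earlier than day 56 − 7 = 49, so patients stopping between days 28 and 49 could still be missed.

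**Conclusion.** The denominator point holds. The only response set defined excludes treated patients never re-evaluated, apart from objective progressors before cycle 1 ends, and the imaging schedule leaves early stoppers without a planned scan. ORR is raised if that set is used and such patients exist. The documents give neither their number nor the responder count, so the bias cannot be computed. The illustrations run from 1.3 to 9.4 points under the stated assumptions, with 2.9 points for the 14-responder, two-lost case.

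The confirmation rule and the 8-week statement are secondary matters of wording. The first could lower ORR on one reading, the opposite direction to the denominator effect.

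Severity is low. ORR is descriptive, no decision rule uses it, and the pCR endpoint and its two-stage design are unaffected.

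**What to change.** 1. In 6.2.6 and 10.2, define the main ORR and its 95% CI over all treated patients with measurable disease at baseline, and count those with no post-baseline assessment as non-responders. Report the 6.2.1 evaluable-set rate as supportive, citing that section.
2. State whether confirmation applies to PR and how a response without a confirming scan is classified. Report best CR/PR up to the last pre-surgical MRI alongside the confirmed rate.
3. Reconcile the 8-week statement in 6.2.3 with the 12-week breast MRI in 5.2.3 and 5.5 and with CT at screening only in 5.5, and say which imaging it covers.

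The cost is a protocol amendment with IRB approval, with no extra patients. Items 1 and 2 need no extra scans. The drawbacks are a somewhat lower reported ORR and slightly more measurement error in the unconfirmed rate. The wording should be settled before response data are examined.

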The subjects enrolled in this trial will be treated with Abemaciclib and Fulvestrant until maximal response is obtained or until patients can tolerate it, following which they will undergo surgical resection with a curative intent. At any point in the study, if patients have signs and symptoms of metastasis, they will undergo systemic scans to seek for metastatic sites. Patients will be undergoing systemic scans to rule out metastasis prior to enrollment in the study. There remains a risk of disease progression while surgery is being delayed. However, Abemaciclib and Fulvestrant has currently been approved for the treatment of metastatic ER+ breast cancer now. We believe that patients will have a relatively lower risk of disease progression while on this treatment since this regimen is standard of care in treating ER+ MBC and also since patients will undergo systemic scans prior to enrollment. Furthermore, the risk of delaying surgical intervention will be described in the informed consent provided to research participants.

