4.5 Duration of Therapy

In the absence of treatment delays due to adverse events, treatment may continue until:

- Maximum response (per investigator discretion based on clinical and/or imaging assessments) is obtained OR
- Disease progression as defined radiographic progression by RECIST v1.1 criteria OR death OR symptomatic progression as clinically determined by the treating physician
- Inter-current illness that prevents further administration of treatment
- Unacceptable adverse event(s)
- Patient decides to withdraw from the study, **OR**
- General or specific changes in the patient's condition render the patient unacceptable for further treatment in the judgment of the investigator

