5.5 Time and Events Table

If baseline evaluations are conducted within 1 week prior to administration of protocol therapy, those assessments do not need to be repeated. Scans must be done \leq 4 weeks prior to the start of therapy. In the event that the patient's condition is deteriorating, laboratory evaluations should be repeated within 48 hours prior to initiation of the next cycle of therapy.

	Baseline/Screening	Treatment Phase		Post-discontinuation		
	-28 to -1 days	Cycle 1	Subsequent cycles	End of Treatment	Surgery	Follow-up

CONFIDENTIAL

This material is the property of the [UC Irvine Chao Family Comprehensive Cancer Center](#). Do not disclose or use except as authorized in writing by the study sponsor.

		D1 (-3d)	D15 (±3d)	D1 (-3d)	Within 30 days of last dose prior to surgery		Every 6 months (±14d)
Assessment							
Informed Consent	X						
History and PE	X	X		X	X		
Vital Signs	X	X	X	X	X		
Baseline medical and oncology history	X						
Concomitant Medications	X	X		X	X		
ECOG Performance Status	X	X		X	X		X
Adverse Events		X		X	X		
Tumor Measurements	X						
CT CAP or CT chest/MRI Abd/Pelvis ¹	X						
MRI Breast	X			X Every 12 weeks (±7d) after first dose until maximum response or progression, whichever occurs first			
CBC w/diff	X	X	X	X	X		
CMP	X	X	X	X	X		
Postmenopausal Confirmation	X						
ctDNA (correlative study)	X			X ²			X
Biopsy ³					X		
Tissue Submission	X				X	X	
Administer Abemaciclib		X	X	X			
Administer Fulvestrant		X	X	X			
Study Drug Accountability				X	X		

¹ CT Chest, abdomen and pelvis with contrast or CT chest/MRI Abdomen, Pelvis is required at screening to rule out metastasis

² Every 3 months during treatment

CONFIDENTIAL

This material is the property of the [UC Irvine Chao Family Comprehensive Cancer Center](#). Do not disclose or use except as authorized in writing by the study sponsor.

³ A fresh biopsy at time of progression is mandatory if clinically feasible.

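### ORR requires a confirmed response, but no scan is scheduled to confirm a response first seen on the last breast MRI before surgery

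*Combined protocol and SAP*

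**What the plan says.** ORR is the first secondary objective (section 2.2.1) and is to be reported with a 95% confidence interval (section 10.2).

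- **Definition.** Section 6.2.6 counts an "objective confirmed overall complete response (CR) or partial response (PR) based on RECIST version 1.1 guidelines".
- **CR.** Section 6.2.4.1 requires disappearance of all target lesions, "determined by two separate observations conducted not less than 4 weeks apart".
- **PR.** The same section requires a decrease of at least 30% in the sum of longest diameters from baseline. It names no second observation.
- **Synopsis.** The Statistical Methodology entry of the Study Summary speaks of "estimating the objective response rate (CR, PR) in the breast and/or the axillary lymph nodes", with no mention of confirmation.
- **Imaging.** The tumor assessment paragraph numbered 5.2.3 and the table in section 5.5 schedule breast MRI every 12 weeks, with a window of 7 days either side, and the table runs it "until maximum response or progression, whichever occurs first". Section 6.2.3 has scans at baseline and "after that every 8 weeks (+/- 7 days) until end of treatment".
- **End of treatment.** The list in section 5.3.2 ("Within 30 days after treatment termination") contains no imaging. The table in section 5.5 marks no MRI under End of Treatment, Surgery or Follow-up.
- **Surgery.** Section 1.4 says treatment continues "until maximal response is obtained or until patients can tolerate it, following which they will undergo surgical resection with a curative intent".
- **Evaluability.** Section 6.2.1 requires measurable disease, at least one cycle, and a re-evaluation. One re-evaluation is enough.

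**The concern.** Confirmation needs a second look at the lesion. In this trial the event that ends treatment, maximum response, also ends the MRI schedule and sends the patient to surgery. The scan on which a response first appears may therefore be the last one planned. Under the literal rule the patient stays in the denominator and cannot enter the numerator unless someone arranges a scan that the protocol does not ask for.

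Whether a response counts would then depend partly on how long treatment ran after it appeared, not only on what the tumor did. The protocol does not say how an unconfirmed response is to be scored. What is at stake is the estimate and interval for a descriptive secondary endpoint.

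**Working it through.** **1. The plan's own design figures.** The plan gives no figure for ORR. Its only design calculation is the Simon two-stage design in section 10.2: 10 patients in stage 1, stop at 1 or fewer responses, 29 in total, reject at 6 or more, p0 = 0.1, p1 = 0.3.

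- Early stopping at p0: P(X ≤ 1 | 10, 0.1) = 0.9^10 + 10 × 0.1 × 0.9^9 = 0.7361.
- Expected size at p0: 10 + (1 − 0.7361) × 19 = 15.01.
- Rejection probability: sum over x = 2 to 10 of P(X1 = x) × P(X2 ≥ 6 − x), with X1 from 10 patients and X2 from 19. This is 0.0471 at p = 0.1 and 0.8051 at p = 0.3.

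All four figures reproduce. The primary endpoint is pCR, so nothing below changes them.

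**2. When a second scheduled scan would fall.**

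| Schedule | First on-treatment scan | Second scan | Shortest gap |
|---|---|---|---|
| 12 weeks ± 7 days | days 77–91 | days 161–175 (weeks 23–25) | 161 − 91 = 70 days |
| 8 weeks ± 7 days | days 49–63 | days 105–119 (weeks 15–17) | 105 − 63 = 42 days |

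Either gap exceeds 28 days, so two consecutive scheduled scans always satisfy the 4-week spacing. Spacing is not the problem. The problem is whether a second scan takes place before treatment stops. On the 12-week schedule, a response first seen on the first scan has its next scheduled look at weeks 23–25, and only if treatment continues that long.

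**3. Whether one scan before surgery is plausible.** The protocol fixes no treatment duration. The neoadjuvant fulvestrant study cited in section 10.0 treated for 16 weeks (day 112) before surgery. On the 12-week schedule that course holds exactly one on-treatment MRI. This shows plausibility only and is not this trial's duration.

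**4. Size.** One responder scored as a failure among 29 lowers ORR by 1/29 = 3.4 points. For illustration, assume 14 responders on MRI among 29 evaluable patients: 0.481 × 29 = 13.9, using the 48.1% that section 10.0 cites for abemaciclib plus fulvestrant in advanced disease. The number unconfirmed is not given, so it is varied. Intervals are exact (Clopper-Pearson) 95%.

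| Unconfirmed | Confirmed ORR | 95% CI |
|---|---|---|
| 0 | 14/29 = 48.3% | 29.4–67.5 |
| 1 | 13/29 = 44.8% | 26.4–64.3 |
| 2 | 12/29 = 41.4% | 23.5–61.1 |
| 3 | 11/29 = 37.9% | 20.7–57.7 |
| 7 (half) | 7/29 = 24.1% | 10.3–43.5 |
| 14 (all) | 0/29 = 0% | 0–11.9 |

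The last row is a bound, not an expectation.

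**The case against.** The strongest reply is that few patients may be affected. Treatment is open-ended and runs to maximum response, and one post-baseline scan can hardly show that shrinkage has stopped. Serial MRIs may be the usual course, and a response at week 12 can be confirmed at week 24. That stands as a limit on frequency. It does not remove the gap: section 4.5 lets treatment end on "Maximum response (per investigator discretion based on clinical and/or imaging assessments) is obtained OR", so a second scan is not required, and patients who stop for tolerability also go to surgery.

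A reader might infer that such a response can never be confirmed. The documents do not support that. Nothing bars an added MRI. Section 6.2.2 lets target lesions be chosen for repeat measurement by imaging or clinically, and physical examinations continue to the end-of-treatment visit. Section 6.2.3 asks for the same method throughout and prefers imaging, which limits the clinical route without closing it. The accurate statement is that no confirmation is scheduled. For a CR, an added scan would also mean waiting at least 4 weeks, and section 1.4 recognizes a risk in delaying surgery.

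A reader might also infer that the protocol holds two rival ORR definitions of equal standing. That goes too far. Section 6.2.6 is the operative definition, and the synopsis is a short summary that omits the qualifier. Section 6.2.6 also defers to RECIST 1.1, so the silence of section 6.2.4.1 on PR does not by itself prove that no PR confirmation rule applies.

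Finally, confirmed ORR is a stricter and defensible endpoint in an open-label single-arm trial, and being lower than unconfirmed ORR is not in itself bias. This also stands in general. Here, though, a response can fail confirmation merely because no further scan was due.

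**Conclusion.** The point holds for a response first seen on the last MRI before surgery. Under the literal text that patient is evaluable and a non-responder, and ORR understates the response achieved before surgery by about 3.4 points per such patient, taking 29 as the denominator. The total effect cannot be stated, because the documents do not say how long treatment will run or how many responses will rest on one scan. In the illustration, three unconfirmed responders move ORR from 48.3% to 37.9%, with widely overlapping intervals. Both the 48.1% starting rate and the counts are assumptions.

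It would be wrong to infer that the trial's main conclusion is at risk. ORR carries no hypothesis test, threshold or stopping rule, and section 10.2 already concedes low power for secondary endpoints. pCR, the sample size and the stage 1 rule are untouched. This is an inexpensive improvement to a descriptive secondary endpoint, best settled before ORR is analyzed.

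**What to change.** In section 6.2.6, define ORR for all evaluable patients as a best overall response of CR or PR against baseline on any on-treatment breast MRI before surgery, with no confirmation required. State there or in section 6.2.4.1 that the two-observation CR rule does not apply to ORR. This agrees with the synopsis. Apply it to every evaluable patient, not only to those who reach surgery. Otherwise one rate would mix confirmed and unconfirmed responses according to something that happens after treatment.

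Label the result as unconfirmed ORR, report how many responses rest on a single MRI, and give confirmed ORR as a sensitivity figure.

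The cost is text edits to two sections and a few lines in the ORR table. No MRI or visit is added, and the sample size, stage 1 rule and pCR definition stay as they are. The downside is slightly more measurement error, which the single-MRI count and the sensitivity figure make visible. The wording of section 4.5 on how maximum response is judged, and the evaluable-only denominator in section 6.2.1, are separate points that this edit does not address.
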